**RESTRICTED**

	SPONSOR: Scandinavian Biopharma Holding AM (SBH)	PROTOCOL NUMBER: OEV-131	PROTOCOL TITLE: Pre-Study of wild type Enterotoxigenic E.coli (ETEC) Strain for Verification of a planned Challenge Dose	VERSION NO: 1.0
				VERSION DATE: 14JUN2024

Variable	Statistic	All Subjects (N=X)
Maximum Weight (g) of Grade 3-5 Stools in 24-Hour Window during 120- Hour Observation Period	Mean	xx.x
	Standard Deviation	xx.x
	Median	xx.x
	Minimum	xx
	Maximum	xx
Maximum Weight (g) of Grade 3-5 Stools in 24-Hour Window during Inpatient Period	Mean	xx.x
	Standard Deviation	xx.x
	Median	xx.x
	Minimum	xx
	Maximum	xx

Note: N = Number of subjects in the Full Analysis Set.

**RESTRICTED**

	SPONSOR: Scandinavian Biopharma Holding AM (SBH)	PROTOCOL NUMBER: OEV-131	PROTOCOL TITLE: Pre-Study of wild type Enterotoxigenic E.coli (ETEC) Strain for Verification of a planned Challenge Dose	VERSION NO: 1.0
				VERSION DATE: 14JUN2024

**Table 15: Time to Primary Endpoint, Unadjudicated Primary Endpoint, and Diarrhea Onset - Full Analysis Set\***

Event	Statistic	All Subjects (N=X)	
		Estimated Time to Event (hours) e	95% CI f
Primary Endpoint a	Minimum	xx	xx.x, xx.x
	25 th Percentile	xx	xx.x, xx.x
	50 th Percentile (Median)	xx	xx.x, xx.x
	75 th Percentile	xx	xx.x, xx.x
	Maximum	xx	xx.x, xx.x
Primary Endpoint (Sensitivity Analysis) b	Minimum	xx	xx.x, xx.x
	25 th Percentile	xx	xx.x, xx.x
	50 th Percentile (Median)	xx	xx.x, xx.x
	75 th Percentile	xx	xx.x, xx.x
	Maximum	xx	xx.x, xx.x
Unadjudicated Primary Endpoint c	Minimum	xx	xx.x, xx.x
	25 th Percentile	xx	xx.x, xx.x
	50 th Percentile (Median)	xx	xx.x, xx.x
	75 th Percentile	xx	xx.x, xx.x
	Maximum	xx	xx.x, xx.x
Diarrhea Onset d	Minimum	xx	xx.x, xx.x
	25 th Percentile	xx	xx.x, xx.x
	50 th Percentile (Median)	xx	xx.x, xx.x
	75 th Percentile	xx	xx.x, xx.x
	Maximum	xx	xx.x, xx.x

**RESTRICTED**

	SPONSOR: Scandinavian Biopharma Holding AM (SBH)	PROTOCOL NUMBER: OEV-131	PROTOCOL TITLE: Pre-Study of wild type Enterotoxigenic E.coli (ETEC) Strain for Verification of a planned Challenge Dose	VERSION NO: 1.0

Notes: N = Number of subjects in the Full Analysis Set.

a Time to primary endpoint is defined as the number of hours from challenge to first grade 3-5 stool that meets at least moderate severity criteria, occurs within a diarrhea episode that began prior to 120 hours post challenge, and is deemed attributable to ETEC by an adjudication committee. Subjects who met the primary endpoint according to the adjudication committee but whose stools did not meet the frequency or weight thresholds for moderate or severe diarrhea will be considered to have met the primary endpoint at time of antibiotic administration.

b Time to primary endpoint for the sensitivity analysis is defined as the number of hours from challenge to first grade 3-5 stool that meets at least moderate severity criteria, occurs within a diarrhea episode that began prior to 120 hours post challenge, and is deemed attributable to ETEC by an adjudication committee. Subjects who met the primary endpoint according to the adjudication committee but whose stools did not meet the frequency or weight thresholds for moderate or severe diarrhea will be considered to have met the primary endpoint at 120 hours post challenge.

c Time to unadjudicated primary endpoint is defined as the number of hours between challenge and the first grade 3-5 stool that passes the frequency or weight threshold of moderate diarrhea and occurs within a diarrhea episode that began prior to 120 hours post challenge.

d Time to diarrhea onset is defined as the number of hours from challenge to first grade 3-5 stool of a subject's first diarrhea episode during the inpatient period.

e Estimated time to event is based on the survival function calculated via Kaplan-Meier methodology. Subjects who did not meet the primary endpoint will be right censored at 120 hours post-challenge or time of discharge from the inpatient unit, whichever is first. Subjects who experienced no diarrhea episodes during the inpatient period will be right censored at the time of discharge from the inpatient unit.

f Confidence intervals are calculated via log-log transformation.

**RESTRICTED**

SPONSOR: Scandinavian Biopharma Holding AM (SBH)	PROTOCOL NUMBER: OEV-131	PROTOCOL TITLE: Pre-Study of wild type Enterotoxigenic E.coli (ETEC) Strain for Verification of a planned Challenge Dose	VERSION NO: 1.0
			VERSION DATE: 14JUN2024

**Table 16: Summaries of ETEC Disease Severity Score - Full Analysis Set**

Score Component	Component Definition	Score a	All Subjects (N=X)
			n (%)
Objective Signs Sub-Score	Vomiting frequency and fever	0	x (xx)
		1	
		2	
Subjective Symptoms Sub-Score	Lightheadedness, nausea, malaise, headache, and abdominal cramps.	0	
		1	
		2	
Stool Output Sub-Score	Diarrhea frequency and volume	0	
		1	
		2	
		3	
		4	
Total Score	Sum of all score components	0	
		1	
		2	
		3	
		4	
		5	
		6	
		7	
		8	

Notes: N = Number of subjects in the Full Analysis Set; n = Number of subjects with the corresponding score for each ETEC disease severity score component.

a Higher scores correspond to more severe ETEC disease.

**RESTRICTED**

SPONSOR: Scandinavian Biopharma Holding AM (SBH)	PROTOCOL NUMBER: OEV-131	PROTOCOL TITLE: Pre-Study of wild type Enterotoxigenic E.coli (ETEC) Strain for Verification of a planned Challenge Dose	VERSION NO: 1.0
			VERSION DATE: 14JUN2024

**Table 17: ETEC Impact on ADLs - Full Analysis Set**

ADL Question	Response	All Subjects (N=X)		
		n	%	95% CI a
If traveling for vacation or business, would you have changed your itinerary?	Yes	x	xx	xx.x, xx.X
	No			
Would you have stayed in bed?	Yes			
	No			

Notes: N = Number of subjects in the Full Analysis Set; n = Number of subjects providing the corresponding response to each question; ADL = Activity of Daily Living.

a Exact binomial confidence interval calculated via Clopper-Pearson methodology.

**RESTRICTED**

	SPONSOR: Scandinavian Biopharma Holding AM (SBH)	PROTOCOL NUMBER: OEV-131	PROTOCOL TITLE: Pre-Study of wild type Enterotoxigenic E.coli (ETEC) Strain for Verification of a planned Challenge Dose	VERSION NO: 1.0
				VERSION DATE: 14JUN2024

**Table 18: ETEC Illness Interventions - Full Analysis Set**

Intervention	All Subjects (N=X)		
	n	%	95% CI a
Early antibiotic treatment (prior to Day 6)	x	xx	xx.x, xx.x
Administration of IV fluids	x	xx	xx.x, xx.x
Notes: N = Number of subjects in the Full Analysis Set; n = Number of subjects who received the corresponding intervention due to ETEC illness.			
a Exact binomial confidence interval calculated via Clopper-Pearson methodology.			

**RESTRICTED**

	SPONSOR: Scandinavian Biopharma Holding AM (SBH)	PROTOCOL NUMBER: OEV-131	PROTOCOL TITLE: Pre-Study of wild type Enterotoxigenic E.coli (ETEC) Strain for Verification of a planned Challenge Dose	VERSION NO: 1.0
				VERSION DATE: 14JUN2024

**Table 19: Qualitative Shedding of the E24377A Challenge Strain by Study Day - Full Analysis Set**

Study Day	Antibiotic Treatment Status b	N	Fecal Culture Result a			
			Positive		Negative	
			n	%	n	%
Any Day	Any Status	xx	xx	xx	xx	xx
	Treated					
	Not Treated					
Day 1	Any Status					
	Treated					
	Not Treated					
Day 2	Any Status					
	Treated					
	Not Treated					
Day 3	Any Status					
	Treated					
	Not Treated					
Day 4	Any Status					
	Treated					
	Not Treated					
Day 5	Any Status					
	Treated					
	Not Treated					
Day 6	Any Status					
	Treated					
	Not Treated					
Day 7	Any Status					
	Treated					
	Not Treated					
Day 8	Any Status					
	Treated					
	Not Treated					
Day 9	Any Status					
	Treated					
	Not Treated					

N = Number of subjects with a fecal culture result on the given study day with the corresponding antibiotic treatment

**RESTRICTED**

	SPONSOR: Scandinavian Biopharma Holding AM (SBH)	PROTOCOL NUMBER: OEV-131	PROTOCOL TITLE: Pre-Study of wild type Enterotoxigenic E.coli (ETEC) Strain for Verification of a planned Challenge Dose	VERSION NO: 1.0

status on that day; n = Number of subjects with the corresponding fecal result and antibiotic treatment status on the given study day.

a Only one fecal culture result is counted per subject per day. If a subject has both positive and negative culture results from fecal samples collected on the same day, then the positive result is counted.

b A subject is considered treated if they received at least one dose of antibiotics prior to sample collection for the reported result. If at least one positive culture result was reported on a given study day, then the antibiotic treatment status prior to the last positive result on that day is reported. If only negative culture results were reported on a given study day, then the antibiotic treatment status prior to the last negative result on that day is reported.

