9.4.8.2 Concomitant therapy during the study

During the study, all subjects will receive a 3-day course of antibiotics.

On the morning of Day 6 (or sooner if the subject met the criteria for early antibiotic treatment; see below), all subjects will start a 3-day course of ciprofloxacin 500 mg BID.

Subjects with an allergy to or who are unwilling to take a fluoroquinolone, may receive azithromycin 500 mg by mouth daily for three days or amoxicillin 500 mg by mouth three times daily for three days.

If, because of illness, a subject is unable to take oral antibiotics, intravenous antibiotics may be given at an appropriate dose based on weight and clinical status.

Criteria for early antibiotic treatment

Subjects meeting any of the following criteria before Day 6 will start antibiotic treatment at that time:

- Severe diarrhea as defined as >800 grams of grade 3-5 stools within a rolling 24 hour-period (see Section 9.5.3.1.2).
- Stool output consistent with moderate diarrhea for 48 hours
- Diarrhea of any severity AND 2 or more of the following symptoms: severe abdominal pain, severe abdominal cramps, severe nausea, severe headache, severe myalgias, severe arthralgia), any fever ($\geq 100.4^{\circ}\text{F}$, 38.0°C), or any vomiting
- Any fever $\geq 102.1^{\circ}\text{F}$ (39.0°C)
- A study clinician determines early treatment is warranted for any other reason

Subjects who meet the criteria for early antibiotic treatment, may be discharged from the in-patient unit earlier than anticipated upon meeting discharge criteria. Discharge criteria include at least 2 stools negative for the challenge organism, having taken at least 2 doses of antibiotics, and have no or improved symptoms.

Subjects taking any other non-antibiotic medication on a chronic basis may continue with that medication unless directed otherwise by a study clinician. All such medication will be collected on admission to the inpatient facility and will be dispensed by study staff until discharge.

Rehydration

Subjects passing grade 3-5 stools post-challenge will be asked to drink liquids, at the same volume as their stool output.

A subject may be administered IV fluids if they:

- Experience abrupt onset of diarrhea, defined as passage of an initial loose/liquid stool of >300 g, or >400 g of loose/liquid stools over 2 hours in conjunction with other symptoms, as determined by PI or designee.

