## 2.7. Microbiology Variable

### 2.7.1. Qualitative Shedding of Challenge Strain

Up to 3 fecal samples per subject per day of the inpatient period will be cultured for presence of the E24377A challenge strain. If no stool is passed, rectal swabs may be collected and cultured. Culture results will be reported as positive or negative for E24377A.

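### SAP Table 19 takes a subject's antibiotic status from the last positive culture of the day, so on antibiotic start days the Treated percentage can be too high and is never too low

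*SAP*

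**What the plan says.** SAP section 2.7.1 allows several cultures a day: "Up to 3 fecal samples per subject per day of the inpatient period will be cultured for presence of the E24377A challenge strain". Table 19 reports them by study day in three rows: Any Status, Treated and Not Treated. The notes to the table set four rules.

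- One result is counted per subject per day. Footnote a: "If a subject has both positive and negative culture results from fecal samples collected on the same day, then the positive result is counted".
- Footnote b defines the status: "A subject is considered treated if they received at least one dose of antibiotics prior to sample collection for the reported result".
- If there was any positive that day, "then the antibiotic treatment status prior to the last positive result on that day is reported". Otherwise the last negative sample decides.
- The denominator follows the same status: "N = Number of subjects with a fecal culture result on the given study day with the corresponding antibiotic treatment".

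Each subject-day therefore has one result and one status, and enters either Treated or Not Treated, never both.

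Every subject receives antibiotics. Protocol section 9.4.8.2 starts the course "On the morning of Day 6 (or sooner if the subject met the criteria for early antibiotic treatment; see below". SAP section 2.6.4 has early starters begin when they meet a criterion, which can be at any hour. SAP section 5.8 adds no further rule for the table.

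**The concern.** Each subject has one day, the antibiotic start day, on which cultures can fall on both sides of the first dose. On that day footnote b lets the culture result decide which row the subject enters. A subject who is still positive after the dose goes to Treated. A subject who was positive before the dose and clears goes to Not Treated, and the post-dose negatives are counted nowhere. The Treated row keeps its positives and loses some of its negatives.

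At stake is how the Treated and Not Treated percentages read on Day 6 and on any earlier start day. Protocol Table 3 reports early antibiotics in 12/15 (80%) and 8 of 16 (50%) subjects in two studies with this lot, so start days may be spread over several study days, with few treated subjects on each. SAP Appendix C plans no listing of stool culture results, so a reader of the report could not rebuild the split.

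**Working it through.** Table 19 is an empty mock-up, so there is no planned figure to reproduce. The check applies the footnotes literally.

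**Which row each pattern enters on a start day with cultures on both sides of the dose**

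| Before first dose | After first dose | Row under footnotes a and b |
|---|---|---|
| any result | at least one positive | Treated, Positive |
| all negative | all negative | Treated, Negative |
| at least one positive | all negative | Not Treated, Positive |

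Only the third pattern has a post-dose culture and is absent from the Treated row. This holds for every ordering of up to three samples.

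**Formula.** For a given study day let P = subjects with a post-dose positive, N0 = subjects with a post-dose sample who are negative all day, and X = subjects positive before the dose and wholly negative after it.

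- Treated row as written: P/(P+N0)
- Treated row with each culture classified at its own time: P/(P+N0+X)

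The first exceeds the second whenever X>0 and P>0. If X=0 they are equal. If P=0 both are 0%, provided the row is not empty. P is the same in both.

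**Numerical check of direction.** Footnotes a and b were applied to 200,000 random cohorts of 2 to 30 subjects with up to three samples each. The Treated row was non-empty in 198,247. It was too high in 147,084, equal in 51,163 and never too low (147,084 + 51,163 = 198,247). These counts reflect arbitrary random patterns and are not probabilities for this trial.

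**Size.** All inputs below are assumed, because the documents do not say how many subjects will have cultures on both sides of the first dose.

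| Assumed case | P | N0 | X | As written | Own-time status |
|---|---|---|---|---|---|
| A. 12 start on Day 6: 6 post-dose positive, 2 cleared, 4 negative all day. 13 treated earlier, still cultured, all negative | 6 | 4+13=17 | 2 | 6/23 = 26% | 6/25 = 24% |
| B. As A, but nobody treated earlier is still cultured | 6 | 4 | 2 | 6/10 = 60% | 6/12 = 50% |
| C. 20 start. 8 have both samples (2 +/+, 4 +/−, 2 −/−). 12 have post-dose only (4 +, 8 −) | 2+4=6 | 2+8=10 | 4 | 6/16 = 37.5% | 6/20 = 30% |
| D. 25 sampled before and after, 20 positive before, 5 negative throughout; 25% of the 20 clear | 15 | 5 | 5 | 15/20 = 75% | 15/25 = 60% |
| E. As D, 50% clear | 10 | 5 | 10 | 10/15 = 67% | 10/25 = 40% |
| F. As D, 75% clear | 5 | 5 | 15 | 5/10 = 50% | 5/25 = 20% |

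Case F is not a bound. With everyone sampled before and after, 90% positive before the dose, and post-dose positivity of 30% (if positive before) or 5% (if negative before), own-time positivity is 0.9×0.30 + 0.1×0.05 = 27.5%. The row would show 0.275/(0.275 + 0.1×0.95) = 74.3%.

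**Not Treated row.** Subjects positive on both sides leave this row and pull it down; subjects negative on both sides leave it and push it up. Compared with the share of subjects positive before the dose, the row was too high in 155,592 of the random cohorts and too low in 15,262, so its direction is not fixed.

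**Any Day rows.** The footnotes are written for a given study day and do not say how status is set across days. If the last-positive rule were carried across days, everyone who shed before treatment and then cleared would leave Treated. For example (assumed), with 25 subjects, 23 positive before, 8 still positive after and 2 never positive, the row would show 8/10 (80%) against 8/25 (32%). The SAP neither states nor excludes this reading.

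**The case against.** The strongest reply is that the secondary microbiology endpoint is unaffected. The endpoint is shedding, positive or negative, after challenge. SAP section 5.8 promises it by study day without mentioning antibiotic status, and the Any Status row delivers it. The Treated split is supplementary, the rule is openly stated, and it keeps the rows mutually exclusive and summing to Any Status. No testing is planned, and no rule in the documents uses the table.

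The size may also be modest. The routine dose is in the morning, so only samples earlier on Day 6 count as pre-dose. If the early-antibiotic shares in Protocol Table 3 carried over to 25 subjects (an assumption), about 5 to 13 would start on Day 6, not all 25. Subjects treated earlier and still cultured would dilute the effect. That dilution is uncertain, because culture stops after two consecutive negatives (Protocol Table 1, footnote 9).

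Most of this stands, and it rules out three stronger readings that a reader might infer.

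- That the table understates how fast antibiotics suppress shedding, and so fails an aim of the study: no objective or endpoint concerns that question.
- That the Not Treated row reads 100%: this occurs in cases D to F only because every subject there has a post-dose culture.
- That 50% against 20% is what to expect on Day 6: it needs every subject to be sampled on both sides of the dose.

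The reply does not rescue the split itself. The SAP chose to print a Treated percentage and defined Treated by a dose before the sample. Stating the convention openly does not make row membership independent of the result.

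**Conclusion.** The point holds as a defect in a stated rule for a descriptive secondary table. On antibiotic start days the Treated percentage is P/(P+N0) where P/(P+N0+X) is wanted. The error goes one way, through the denominator. The Not Treated row is distorted too, in no fixed direction.

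The size cannot be fixed from the documents. Under the assumed inputs it runs from 2 percentage points (26% against 24%) through 7.5 points (37.5% against 30%) to 30 points (50% against 20%) when everyone is sampled on both sides of the dose.

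It is confined to one day per subject: from the next day on, all of that subject's samples are post-dose and correctly placed. The Any Status rows and the primary endpoint are untouched. Whether the Any Day status rows are affected depends on a rule the SAP does not give.

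**What to change.** Rewrite footnote b of SAP Table 19:

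1. Classify each culture as Treated or Not Treated by whether a dose was taken before that sample was collected.
2. Let a positive outrank a negative within subject, day and status. On the start day a subject may then count once in each status row.
3. Keep one result per subject-day for Any Status.
4. State the same rule for the Any Day rows.
5. Add a note that the Treated and Not Treated Ns may sum to more than Any Status.

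The cost is a footnote and one programming change. The present rule already needs sample and dose times, so no new data are required. The small downside is that the two status rows no longer add up to Any Status on start days, or in the Any Day rows.

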**RESTRICTED**

	SPONSOR: Scandinavian Biopharma Holding AM (SBH)	PROTOCOL NUMBER: OEV-131	PROTOCOL TITLE: Pre-Study of wild type Enterotoxigenic E.coli (ETEC) Strain for Verification of a planned Challenge Dose	VERSION NO: 1.0
				VERSION DATE: 14JUN2024

#### 14.4 Concomitant Medications

**Table 20: Number and Percentage of Subjects with Prior and Concurrent Medications by WHO Drug Classification - Full Analysis Set**

WHO Drug Code Level 1, Anatomic Group	WHO Drug Code Level 2, Therapeutic Subgroup	All Subjects (N=X)	
		n	%
Any Level 1 Codes	Any Level 2 Codes	x	xx
[ATC Level 1 - 1]	Any [ATC 1 – 1]		
	[ATC 2 - 1]		
	[ATC 2 - 2]		
	[ATC 2 - 3]		
[ATC Level 1 – 2]	[ATC 2 - 1]		
	[ATC 2 - 2]		
	[ATC 2 - 3]		

Note: N = Number of subjects in the Full Analysis Set; n = Number of subjects reporting taking at least one medication in the specific WHO Drug Class.

**RESTRICTED**

SPONSOR: Scandinavian Biopharma Holding AM (SBH)	PROTOCOL NUMBER: OEV-131	PROTOCOL TITLE: Pre-Study of wild type Enterotoxigenic E.coli (ETEC) Strain for Verification of a planned Challenge Dose	VERSION NO: 1.0
			VERSION DATE: 14JUN2024

## 14.3 Safety Data

### 14.3.1 Displays of Adverse Events

**Table 21: Overall Summary of Adverse Events - Full Analysis Set**

		All Subjects (N=X)	
Event Category a		Subcategory a	n
At least one ETEC disease-specific solicited event	Any Severity	x	x
	Mild (Grade 1)		
	Moderate (Grade 2)		
	Severe (Grade 3)		
	Potentially Life-Threatening (Grade 4)		
At least one unsolicited adverse event	--		
At least one unsolicited adverse event related to challenge	Any Severity		
	Mild (Grade 1)		
	Moderate (Grade 2)		
	Severe (Grade 3)		
	Potentially Life-Threatening (Grade 4)		
At least one unsolicited adverse event related to study procedure	Any Severity		
	Mild (Grade 1)		
	Moderate (Grade 2)		
	Severe (Grade 3)		
	Potentially Life-Threatening (Grade 4)		
At least one unsolicited adverse event related to antibiotics	Any Severity		
	Mild (Grade 1)		
	Moderate (Grade 2)		
	Severe (Grade 3)		
	Potentially Life-Threatening (Grade 4)		
At least one severe (Grade 3) unsolicited adverse event	Any Relationship to Challenge		
	Related to Challenge		
	Not Related to Challenge		
At least one serious adverse event b	--		
At least one serious adverse reaction b	--		
At least one suspected unexpected serious adverse reaction	--		

**RESTRICTED**

DOCUMENT REF.: SOP-ST-01  
LAST REVISION DATE: N/A  
VERSION NO.: 1.0

DOCUMENT NAME:  
**Statistical Analysis Plan**

SPONSOR: Scandinavian Biopharma Holding AM (SBH)	PROTOCOL NUMBER: OEV-131	PROTOCOL TITLE: Pre-Study of wild type Enterotoxigenic E.coli (ETEC) Strain for Verification of a planned Challenge Dose	VERSION NO: 1.0
			VERSION DATE: 14JUN2024

		All Subjects (N=X)	
Event Category a	Subcategory a	n	%
At least one adverse event leading to early termination c	--		
At least one new chronic illness	--		
At least one adverse event of special interest d	--		

Notes: N = Number of subjects in the Full Analysis Set; n = Number of subjects with the corresponding event.

a Subjects are counted once for each subcategory regardless of the number of events.

b A listing of Serious Adverse Events is included in Section 9.3.6.

c As reported on the Adverse Event eCRF.

d Adverse events of special interest (AESIs) may include the development of Irritable Bowel Syndrome or other continuing gastrointestinal condition.

